3. STUDY OBJECTIVES AND ENDPOINTS

The objective of this study is to evaluate the safety and preliminary efficacy of ATYR1923, compared to placebo, in subjects with SARS-CoV2-related severe pneumonia not requiring mechanical ventilation.

3.1. Primary

The primary objective is:

- To assess the safety of a single intravenous (IV) dose of ATYR1923. Safety will be assessed by:
 - Incidence of TEAEs, including serious and severe TEAEs, overall and by severity.

3.2. Secondary

Secondary objective is:

- To assess the preliminary effects of ATYR1923 on clinical outcome measures of SARS-CoV-2 infection, including:
 - Time to hospital discharge.
 - Time to recovery (World Health Organization [WHO] Ordinal Scale score ≤ 3).
 - Proportion of patients achieving recovery by Day 14 and Day 28.
 - Duration of supplemental oxygen (O_2) requirement.
 - Number of days with fever (temperature $>100.4^{\circ}\text{F}$ [38.0°C]).
 - Change from baseline in WHO Ordinal Scale score on Days 5, 7, 14, 28, and 60.
 - Time to improvement from inpatient hospital admission based on at least a 1 point reduction in WHO Ordinal Scale score.
 - All-cause mortality at Days 14, 28, and 60.

3.3. Exploratory

The exploratory objectives are:

- To explore the preliminary efficacy of ATYR1923 for SARS-CoV-2 infection by evaluating effects on the following:
 - Change from baseline in supplemental oxygen requirement at Days 3, 5, 10, 14 and discharge.
 - Proportion of patients requiring intubation, and among those patients, number of days of intubation.
- To assess the pharmacodynamics (PD) of a single IV dose of ATYR1923 by measuring inflammatory biomarkers and cytokines including: C-reactive protein (CRP), interferon

gamma (INF- γ), interleukin (IL)-6, IL-2, IL-7, IL-10, tumor necrosis factor-alpha (TNF α), macrophage inflammatory protein-1 (MIP1), C-X-C motif chemokine 10 (CXC-10), and monocyte chemoattractant protein-1 (MCP-1).

- To assess the impact of a single IV dose of ATYR1923 by measuring potential markers of COVID-19 disease, including serum ferritin and D-dimer.

4. INVESTIGATIONAL PLAN

4.1. Overall Study Design and Plan

Study ATYR1923-C-003 is a randomized, double-blind, placebo-controlled study to evaluate the safety, PD and efficacy of ATYR1923 in subjects with SARS-CoV-2 related severe pneumonia. SARS-CoV-2 infection will be confirmed using a polymerase chain reaction (PCR) based test during Screening. The Investigator, Sponsor, and patient will be blinded to treatment assignment; study center pharmacy personnel will be unblinded.

Eligible patients will be randomized 1:1:1 to a single IV dose of ATYR1923 1 mg/kg, ATYR1923 3 mg/kg, or placebo. Study drug (ATYR1923 or placebo) will be added onto institutional standard of care (SOC) for treating SARS-CoV2 infection.

A single dose of study drug will be administered on Day 1. All study drug will be administered in the hospital setting; patients who are intubated after randomization but prior to study drug administration are no longer eligible to receive study drug. As this is a single-dose study, the treatment period is 1 day. Thereafter, all patients will be followed for 60 days post-treatment. The schedule of study assessments over this period is dependent on the duration of hospitalization and whether or not the patient requires intubation.

- ***While hospitalized***, non-intubated patients will have study assessments performed on Days 2, 3, 4, 5, 6, 7, 10, and Day 14 and/or Discharge.
 - If the non-intubated patient is discharged prior to Day 14, the assessments scheduled for Day 14 and/or Discharge will be completed at the time of discharge. If discharge occurs on another scheduled study assessment day (ie, any day between Day 2 and 10), the Day 14 and/or Discharge assessments supersede that study assessment day and the patient then will proceed to outpatient telephone contact (TC) follow-up visits.
 - If a patient is discharged prior to Day 14, then outpatient TC follow-up visits are to be conducted on Day 7 (as applicable) and Day 14.
 - If the non-intubated patient is discharged on Day 15-20, the patient is to have the assessments scheduled for Day 14 and/or Discharge performed on the day of discharge. If the patient is hospitalized for ≥ 21 days, the Day 14 assessments are to be performed weekly (Days 21, 28, 35, etc.) until discharge (with the exception of PK, which is to be done only at Day 28). After discharge, the patient will proceed to the next scheduled outpatient TC follow-up visit. (Thus, if a patient remains hospitalized on Day 28, the Day 28 TC follow-up visit need not be conducted.)

- ***In the event a patient is intubated***, SOC assessments and interventions will supersede study assessments for the duration of their intubation², with clinical assessments collected as available per the institution's electronic medical records (see [Section 4.1.1](#)).
 - Intubated patients will resume the study assessment schedule upon extubation. (Thus, for example, if an intubated patient is extubated, they will resume the study assessment schedule on Day 7).
 - Extubated patients will have the assessments scheduled for Day 14 and/or Discharge performed at the time of hospital discharge and will attend Day 28 and 60 TC follow-up visits.
 - If the patient is hospitalized for ≥ 21 days, assessments (outlined in [Section 4.1.1](#)), are to be performed weekly (Days 21, 28, 35, etc.) until discharge (with the exception of PK, which is to be done only at Day 28). After discharge, the patient will proceed to the next scheduled outpatient TC follow-up visit. (Thus, if a patient remains hospitalized on Day 28, the Day 28 TC follow-up visit need not be conducted.)

An independent Data Safety Monitoring Board (DSMB) will review the progress of the study and perform interim reviews of safety data at regular intervals beginning after the 6th patient has been dosed, and at a frequency guided by the enrollment rate and DSMB recommendation.

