### 3.1.1 Hospitalized, Non-intubated Patients

**While hospitalized**, non-intubated patients will have study assessments performed on Days 2, 3, 4, 5, 6, 7, 10, and 14 and/or Discharge.

If the non-intubated patient is discharged prior to Day 14, the assessments scheduled for Day 14 and/or discharge will be completed at the time of discharge. If discharge occurs on another scheduled study assessment day (ie, any day between Days 2 and 10), the Day 14 and/or discharge assessments supersede that study assessment day and the patient then will proceed to outpatient telephone contact (TC) follow-up visits. If a patient is discharged prior to Day 14, then outpatient TC follow-up visits are to be conducted on Day 7 (as applicable) and Day 14.

If the non-intubated patient is discharged on Days 15-20, the patient is to have the assessments scheduled for Day 14 and/or discharge performed on the day of discharge. If the patient is hospitalized for  $\geq 21$  days, the Day 14 assessments are to be performed weekly (Days 21, 28, 35, etc.) until discharge (with the exception of pharmacokinetics [PK], which is to be done only at Day 28). After discharge, the patient will proceed to the next scheduled outpatient TC follow-up visit. (Thus, if a patient remains hospitalized on Day 28, the Day 28 TC follow-up visit need not be conducted.)

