#### **Analysis Visit Window:**

By visit summaries will be based on the nominal/scheduled visit as reported in eCRF and will be grouped by Day 1, 2, 3, 4, 5, 6, 7, 10, 14, 28 and 60.

For (telephone contact) TC follow up visits and unscheduled Discharge visits, analysis visit windows will be applied as in [Table 2](#) and [Table 3](#) below. Note, analysis visit windows are only used for by visit summaries, not for time to event calculation which will be based on actual date of data collected. TC follow up visits and Discharge visits that are not in any of the analysis visit windows, will be excluded from summaries and only presented in listings.

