**Table 3 Analysis Visit Window for unscheduled Discharge visits**

mapped to	Visit Window
Day 7	Day 8
Day 10	Day 10 ± 1 days
Day 14	Day 14 ± 2 days
Day 28	Day 28 ± 5 days
Day 60	Day 60 ± 5 days

In case several outcomes are available for the nominal/scheduled analysis visits, the latest non-missing result will be used for summaries.

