Days with fever up to Day 14 will be used as a sensitivity analysis. Days will be calculated the same as described for Days of supplemental oxygen (O2) up to Day 14.

Change from baseline in WHO Ordinal Scale score

The description of the WHO Ordinal Scale score is shown in [Section 6.2](#). The Number and percentage of patients on WHO Scale scores and change from baseline (-7, -6, -5, -4, -3, -1, 0, 1, 2, 3, 4) will be presented by visit. Shift table will be presented by visit as well.

Simple Ordinal logistic regression on the WHO Scale score at each visit (Days 5, 7, 14, 28, and 60) will be performed to compare ATYR1923 1 mg/kg versus Placebo and ATYR1923 3 mg/kg versus Placebo. Firth logistic regression ([Firth, 1993](#)) on the collapsed WHO Ordinal Scale (0-3 versus 4-8) at each visit (Days 5, 7, 14, 28, and 60) will be performed as well.

Distribution of WHO Ordinal Scale at 1, 2, 3, 4, 5, 6, 7, 10, 14, 28 and 60 days will be visualized by treatment group using an stacked bar chart. These figures will only consider scheduled assessments and in case the scheduled assessment is not available the mapped unscheduled TC follow up assessments as defined in [Section 4.2](#).

Time to Improvement in Clinical Status

Time to improvement in days is the time in which the patient sees a decrease after study treatment in the WHO Ordinal Scale score from baseline by at least 1 point, derived as:

date of decrease in WHO scale compared to baseline by at least 1 point - study drug administration date; or date of discharge from hospital - study drug administration date, whichever occurs first.

In the case that a patient has not decreased in the WHO scale or withdraws from the study, they will be censored at EOS date. Time to improvement will be analyzed using the Kaplan-Meier methods and Cox Proportional Hazards model as described in the above.

Repeat analysis above for improvement of WHO Ordinal Scale score by at least 2 points.

Additionally, time to improvement will be analyzed using an adapted derivation: date of decrease in WHO scale compared to baseline by at least 1 point - randomization date; or date of discharge from hospital - randomization date, whichever occurs first.

Related output will be noted as sensitivity analysis.

Time to improvement (by at least 1 and 2 points) will be analyzed based on mITT and EE Set. Sensitivity analysis for time to improvement will be analyzed based on mITT only.

*All-cause mortality*

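### As written, SAP Table 3 gives no window to a Discharge visit on Days 2 to 7, so WHO scores taken on Day 5 (and on Day 7, unless a telephone contact fills the gap) in patients going home that day fall out of those days' analyses

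*Protocol*

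**What the plan says.** Protocol 4.1 makes the Discharge assessment replace the visit due that day: "the Day 14 and/or Discharge assessments supersede that study assessment day". This applies to discharges on scheduled days from Day 2 to Day 10. SAP 3.1.1 has the same rule: "discharge assessments supersede that study assessment day and the patient then will proceed to outpatient telephone contact (TC) follow-up visits". The protocol's Schedule of Assessments has one combined Day 14/Discharge column, and the WHO score is collected in it.

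SAP 4.2 (Analysis Visit Window) then sets out how records reach an analysis day:

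- The default is the label on the form: "By visit summaries will be based on the nominal/scheduled visit as reported in eCRF".
- Telephone and certain Discharge visits are windowed: "For (telephone contact) TC follow up visits and unscheduled Discharge visits, analysis visit windows will be applied".
- Anything left over is listed only: "TC follow up visits and Discharge visits that are not in any of the analysis visit windows, will be excluded from summaries".

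Table 3, titled "Analysis Visit Window for unscheduled Discharge visits", maps Day 8 to Day 7, Days 9 to 11 to Day 10, Days 12 to 16 to Day 14, Days 23 to 33 to Day 28 and Days 55 to 65 to Day 60. Table 2 maps telephone contacts on Days 5 to 9 to Day 7.

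The analyses that depend on this are in SAP 4.9.4.1, under change from baseline in WHO score: "Simple Ordinal logistic regression on the WHO Scale score at each visit (Days 5, 7, 14, 28, and 60) will be performed". Firth regressions of the collapsed scale run on the same days, with by-visit shift tables. SAP 4.3.1 does not impute missing scores.

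**The concern.** Taken together, these rules can discard a score measured on exactly the analysis day. A patient discharged on Day 7 has a Day 7 score, but under a Discharge label that Table 3 does not accept, while a Discharge score from Day 8 does count for Day 7. The Day 10 and Day 14 rows include their own target day; the Day 7 row does not, and Day 5 has no row.

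The patients affected are those judged fit to leave that day. Their absence is related to outcome, and with 10 patients per arm a single loss moves a proportion or an odds ratio visibly. Change in WHO score at Days 5 and 7 is part of a listed secondary endpoint.

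**Working it through.** The documents state no figure to reproduce: there is no power calculation, and 30 patients at 1:1:1 gives 10 per arm. The check has three parts.

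**1. Every discharge day against Table 3**

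| Discharge day | Analysis day under Table 3 |
|---|---|
| 2, 3, 4, 5, 6, 7 | none |
| 8 | 7 |
| 9–11 | 10 |
| 12–16 | 14 |
| 17–22 | none |
| 23–33 | 28 |
| 34–54 | none |
| 55–60 | 60 |

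Of the scheduled in-hospital days (2, 3, 4, 5, 6, 7, 10, 14), only 10 and 14 lie inside a window. The gaps at Days 17–22 and 34–54 contain none of the WHO regression days (5, 7, 14, 28, 60), so no same-day regression score is lost there. The gap at Days 2–7 contains two of them.

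**2. Whether a telephone contact can substitute**

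- Day 5: no telephone visit is scheduled, and the earliest Table 2 window maps to Day 7. Nothing can fill Day 5.
- Day 7: Protocol 4.1 plans a Day 7 call after early discharge where applicable, without defining when it applies. A call on Days 5 to 9 fills Day 7. Discharges on Days 2 to 6 can therefore be covered at Day 7. A Day 7 discharge is covered only if a call is also made by Day 9; the next definite call, on Day 14, is too late.

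**3. Size, under stated assumptions**

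Assume exponential time to discharge with median M of 5 to 10 days and λ = ln 2 / M. Expected discharges in the one-day interval ending at a visit are 30 × [exp(−λk) − exp(−λ(k+1))], with k = 3 for Day 5 and k = 5 for Day 7 (dosing on Day 1 is time 0).

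- Day 5: M = 5 gives 30 × (0.660 − 0.574) ≈ 2.6; M = 10 gives 30 × (0.812 − 0.758) ≈ 1.6.
- Day 7: M = 5 gives 30 × (0.500 − 0.435) ≈ 1.9; M = 10 gives 30 × (0.707 − 0.660) ≈ 1.4.

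Per arm of 10 this is under one patient on either day (Day 5: about 0.5 to 0.9; Day 7: about 0.5 to 0.6).

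Effect on one arm, assuming 5 of 10 truly at score ≤3 on Day 5 and dropped patients all among those 5:

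| Dropped | Observed cases | All 10 kept in denominator |
|---|---|---|
| 0 | 5/10 = 50% | 50% |
| 1 | 4/9 = 44% | 4/10 = 40% |
| 2 | 3/8 = 38% | 3/10 = 30% |
| 3 | 2/7 = 29% | 2/10 = 20% |

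The last column applies where the SAP 4.3.1 rule keeps all patients in the denominator.

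Effect on a comparison, with both arms truly 5/10 (odds ratio 1.0) and one active patient dropped:

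- dropped patient at score ≤3: (4/5)/(5/5) = 0.80;
- dropped patient at score ≥4: (5/4)/(5/5) = 1.25.

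The sign depends on the score the patient carried on the day of discharge.

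**The case against.** The best defence is the word *unscheduled* in SAP 4.2 and in the title of Table 3. Days 2 to 7 are all scheduled days, so Day 8 is the first unscheduled one. A Day 7 row that takes only Day 8, with nothing for Days 2 to 7, is what an author might write if scheduled-day discharges kept their nominal day. The eCRF is not among the documents, so its labelling of these visits cannot be checked. This reading is plausible, but the SAP does not state it. It also fits poorly with the superseding rule, the combined Day 14/Discharge column, the exclusion sentence (which covers Discharge visits without that qualifier) and the Table 3 rows that include scheduled Days 10 and 14.

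Three stronger inferences are tempting, and the documents do not support them:

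- **That a Day 7 discharge can never have a Day 7 value.** A call made by Day 9 would supply one.
- **That the bias must run against the better arm.** SAP 4.9.4.1 says some patients left hospital still on oxygen and has rules for a score ≥4 on the discharge day. Dropping such scores pushes the other way.
- **That the distortion is large.** An example with three Day 7 discharges in one arm of 10 is easy to build, but under the exponential assumption above its probability in a given arm is only about 1.0% to 2.3%.

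The reach is also limited. Time-to-event endpoints use actual dates, recovery by Days 14 and 28 counts discharge as recovery, and SAP 4.9.2 treats all p-values as exploratory.

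**Conclusion.** The point holds on the literal text, as a defect in the visit mapping. Day 5 discharge scores are excluded from the Day 5 regressions and shift table with no substitute; Day 7 discharge scores are excluded from Day 7 unless a telephone contact falls in the window. A reader might conclude that these scores are certain to be dropped, but that goes too far because the title of Table 3 allows another reading. At the least, two programmers could build different Day 5 and Day 7 datasets from the same SAP.

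The missingness is informative because discharge causes it. It probably disadvantages the arm discharging faster. Neither direction nor size can be fixed from the documents: they give no discharge-day distribution and do not say how many patients left with a score ≥4. The estimate of roughly one to three patients per day across the trial rests on the assumed exponential distribution and median. The damage is confined to by-visit results, with the WHO regressions affected at two of five time points of one secondary endpoint. It is worth correcting, but it does not threaten the trial's main conclusions.

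**What to change.** Amend SAP 4.2 and Table 3 so that a Discharge assessment on Day 2, 3, 4, 5 or 6 maps to its own study day, and one on Day 7 or 8 maps to Day 7. Use these values in the by-visit tables, the Day 5 and Day 7 ordinal and Firth regressions, and the stacked bar chart. The chart's rule needs its own edit, because it now admits only scheduled assessments and mapped telephone contacts. With this change every discharge day from 2 to 16 has a window. If the eCRF already stores scheduled-day discharges under the nominal day, the SAP should say so.

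The work is a few table rows and two sentences, using scores the schedule already collects. The real cost is timing. SAP versions 2.0 and 3.0 already contain post-unblinding modifications, and this would be another one touching an efficacy endpoint, probably in favour of the faster-discharging arm. It should be disclosed as post-unblinding, labelled post hoc under SAP 3.2 if made after database lock, and reported with results under both mappings.

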4.1.1. Assessments During Intubation

In the event that a patient requires intubation, SOC assessments and interventions will supersede study assessments for the duration of intubation, with the exception of the WHO Scale and sample collection for ADA and Jo-1 Ab, which will continue to be collected as per the Schedule of Assessments ([Table 1](#)) on Days 5, 7, 10, 14 and weekly thereafter. The following clinical assessments will be collected and analyzed as available per the institution's electronic medical records.

- Date and time of intubation and extubation.
- Adverse events (AEs) (including new infections). In the case of new infections, the site and source of culture are to be recorded.
- Concomitant medications.

Patients requiring intubation will have the assessments scheduled for Day 14 and/or Discharge performed at the time of hospital discharge and will attend Day 28 and 60 TC follow-up visits.

2 With the exception of the WHO Scale and sample collection for ADA and Jo-1 Ab, which will continue to be collected as per the Schedule of Assessments.

If the patient is hospitalized for ≥ 21 days, the Day 14 and/or Discharge assessments are to be performed weekly (Days 21, 28, 35, etc.) until discharge (with the exception of PK, which is to be done only at Day 28).

After discharge, the patient will proceed to the next scheduled outpatient TC follow-up visit. (Thus, if a patient remains hospitalized on Day 28, the Day 28 TC follow-up visit need not be conducted.)

4.1.2. Study Completion

The study will be considered complete when the last patient completes the Day 60 TC Follow-up visit and any necessary follow-up for Jo-1 Ab positivity or ongoing study drug-related TEAEs has been completed.

4.2. Discussion of Study Design

Single and repeated doses of ATYR1923 were found to be safe and well tolerated in healthy volunteers and patients with pulmonary sarcoidosis. No significant immunogenic responses (induction of ADAs or Jo-1 Ab positivity) were observed following the administration of single or repeated doses of ATYR1923. The PK of a single dose of ATYR1923 was well characterized and demonstrated dose-proportional exposures over the range of doses from 0.03 to 5 mg/kg following IV drug administration. Terminal elimination phases were parallel, and the mean half-life was consistent from the 0.1 mg/kg onwards, with mean values ranging from 167 to 242 hours.

These data support the continued clinical evaluation of ATYR1923, a novel molecular entity that acts as an extracellular immunomodulator and is under development for treatment of ILD. A strong scientific rationale exists to investigate ATYR1923 as a treatment for patients with severe pneumonia related to SARS-CoV-2 infection (COVID-19), a heavily compromised patient population representing a significant unmet medical need.

Several design features have been employed in the current study in an effort to minimize bias, including a double-blind design, with patients randomized to treatment with ATYR1923 1 mg/kg, 3 mg/kg, or placebo. Random assignment of patients avoids bias and helps ensure that both known and unknown risk factors are distributed evenly between treatment groups. The use of placebo control permits prospective comparison between the ATYR1923 groups and the control group.

This study will be conducted at multiple-study centers. This multi-center design is needed not only for efficient enrollment of the required number of patients, allowing for a more efficient evaluation of ATYR1923, but it provides a better basis for the subsequent generalization of study findings (ICH, 1998).

The current study is specifically designed, with the inclusion of detailed safety measures, to evaluate these parameters in patients with severe pneumonia related to SARS-CoV-2 infection (COVID-19).

Patients will be evaluated for 60 days after study drug exposure.

The development of humoral immune responses (formation of Ab) to exogenously administered proteins occurs commonly. ATYR1923 is a protein-based therapeutic; specifically, it is a human 59-amino acid protein (ie, iMod) directly fused to the C-terminus Fc region of human IgG1, and exists as an Fc fusion dimer. The immunogenicity assessments in clinical ATYR1923 studies include assessment of both ADA and Jo-1 Ab, the Ab that recognizes HARS, with loss of immune tolerance to HARS being associated with anti-synthetase syndrome. No significant immunogenic responses (persistent induction of ADAs or Jo-1 Ab positivity) have been observed in patients participating in an ATYR1923 clinical study to date. However, ADA have occurred infrequently in nonclinical studies with ATYR1923 in the rat and non-human primate. ADA did not affect the PK of the drug. Thus, ADAs may be observed in the current clinical study. Accordingly, the study design includes ADA and Jo-1 Ab testing, detailed clinical monitoring for adverse immunological events, extended safety follow-up if indicated to follow-up on serological findings, and a specific plan to assist Investigators in the clinical management of patients in whom immunogenicity occurs (see [Section 9.9](#)).

The Investigator will take all the usual medical safety precautions necessary for studies at an early stage in the development of a new drug and has full discretion to stop study drug infusion at any time, if clinically warranted, or otherwise in the patient's best interest ([Section 6.4](#)).

